7.1.2 Mycophenolate Mofetil

MMF has been associated with GI toxicity, including nausea, vomiting, abdominal pain and diarrhea, not related to GVHD. If symptoms occur, work up for GVHD should occur. A dose reduction may be instituted for 48-72 hours. If GI toxicity does not resolve within 48-72 hours of stopping the study drug, toxicity is likely not related to the study medication and the drug should be restarted. MMF has also been associated with myelosuppression. If the ANC remains or decreases to less than 1000/ul after engraftment, MMF may be reduced or held at the physician's discretion. Dose adjustments are based on the clinical judgment of the treating physician after considering clinical toxicity and GVHD.

7.1.3 Methotrexate

MTX WILL NOT be dose adjusted or held for neutropenia. MTX may be held or dose reduced if creatinine clearance is decreased by > 50% baseline, if the patient is experiencing clinical signs of veno-occlusive disease, and if the patient has severe mucositis (oral ulceration, significant edema) compromising respiratory function or necessitating parenteral hyperalimentation. Further guidelines for dose adjustments for liver and renal toxicity are as follows:

Dose adjustments for liver toxicity:

Bilirubin (mg/dl)	MTX dose
< 3.0	100%
3.1 -5.0	50%
> 5.0	hold MTX

Dose adjustment for renal toxicity:

Creatinine clearance (ml/min)	MTX dose
> 50	100%
10 – 50	50%
< 0	hold MTX

When creatinine clearance is \leq 60 ml/minute, administer Leucovorin at a dose of 1:1 (Leucovorin:Methotrexate) IV once, 24 hours after the dose of MTX.

Patients with pleural, pericardial or ascetic effusion(s) must be monitored closely for increased duration of MTX toxicity (mucositis and renal insufficiency) and considered for leucovorin therapy.

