6.0 TREATMENT PLAN

6.1 Agent Administration

6.1.1 Tacrolimus (Tac) Administration:

Patients in both group A and B will receive Tac 0.03 mg/kg/day intravenously beginning on day -1 or tacrolimus 0.03mg/kg/dose BID orally beginning on day -3. If Tac is administered intravenously, it will be given over 24 hours and will be converted to oral administration 2 times a day when the patient has engrafted and/or can tolerate oral medication.

Levels of Tac will be obtained to maintain a recommended target serum level of 5-15 mg/mL or per institution guidelines. Dose adjustments of Tac will be made according to Section 7.1.1 below.

In the absence of GVHD, Tac may start to be tapered approximately at day +100 and should be tapered off by day +180, per investigator's discretion.

6.1.2 Mycophenolate Mofetil (MMF) Administration:

Patients in group B only will receive MMF beginning on day +1. Patients ≥ 40 kg will receive MMF 1000 mg twice a day. MMF should be given orally twice a day. IV formulation may be used if the patient cannot tolerate oral route. Patients < 40 kg will receive MMF 45 mg/kg/day (15 mg/kg three times a day). MMF may be given orally or intravenously as per institutional protocol

In the absence of GVHD, MMF may be tapered after day +45 and stopped by day +100 at the discretion of the physician and per institutional guidelines for taper.

6.1.3 Methotrexate (MTX) Administration:

Group A

MTX will be given at 15 mg/m² IV on day +1. Then MTX will be given at 10 mg/m² on days +3, +6 and +11. Dose adjustments of MTX will be made according to Section 7.1.3 below.

If patient < 10 kg then MTX will be given at 0.5 mg/kg IV on day +1. Then MTX will be given at 0.33 mg/kg on days +3, +6 and +11.

Group B

MTX will be given at 5 mg/m² IV on days +1, +3 and +6.

If patient < 10 kg then MTX will be given at 0.17 mg/kg on days +1, +3 and +6.

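### As printed, the methotrexate renal table holds the drug only at a creatinine clearance below 0 ml/min, so 0 to below 10 ml/min has no assigned dose

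*Combined protocol and SAP*

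**What the plan says.** Section 7.1.3 has three pieces of renal text on MTX.

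- A sentence ahead of the tables: "MTX may be held or dose reduced if creatinine clearance is decreased by > 50% baseline". It is permissive, relative to the patient's own baseline, and offers two actions without choosing between them.
- The table introduced as "Dose adjustment for renal toxicity", in ml/min: above 50, 100% of the dose; 10 to 50, 50%; below 0, hold.
- A rescue rule for clearance of 60 ml/min or less: "administer Leucovorin at a dose of 1:1 (Leucovorin:Methotrexate) IV once, 24 hours after the dose of MTX". It applies after a dose has been given and does not hold MTX.

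Section 7.1.3 introduces its liver and renal tables as guidelines. Section 6.1.3, under Group A, refers to them in firmer terms: "Dose adjustments of MTX will be made according to Section 7.1.3 below". The Group B paragraph carries no such reference, but Section 7.1.3 itself is not limited to one arm.

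The liver table beside it has rows for bilirubin below 3.0 mg/dl (100%), 3.1 to 5.0 (50%) and above 5.0 (hold).

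**The concern.** A dose table should give one instruction for every value a patient can have. This one gives none where clearance is lowest, and the row meant to stop the drug cannot be met. Someone applying it on days +1 to +11 to a patient with a clearance of 5 ml/min would have to choose between full dose, half dose and no dose. The table has already halved the dose at 10 to 50.

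The protocol expects renal injury. Section 8.1.3 lists nephrotoxicity among the MTX reactions. Section 8.1.1 names renal insufficiency as a primary toxicity of tacrolimus, which both arms receive. Section 11.1.5 counts dialysis dependence as renal dysfunction. Sections 4.1 and 4.2 set no explicit creatinine or clearance limit for entry, although uncontrolled medical illness is an exclusion. What is at stake is the safe dosing of a patient with severe renal impairment.

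**Working it through.** No sample size, power or alpha figure is involved. The check is whether the rows cover every possible value.

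**1. Renal table as printed.** Possible values: clearance of 0 ml/min or more.

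| Row | Values covered | Possible values in the row | Action |
|---|---|---|---|
| 1 | above 50 | all above 50 | 100% |
| 2 | 10 to 50 | 10 to 50 inclusive | 50% |
| 3 | below 0 | none | hold |

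Rows 1 and 2 together cover 10 and above. Row 3 adds nothing. The uncovered set is 0 to below 10 ml/min.

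**2. Does the baseline sentence fill the gap?** Let B be baseline clearance and c the current value. The sentence applies when c is below B/2. For it to apply at every c below 10, B/2 must be at least 10, so B must be at least 20 ml/min.

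- Baseline 20 or higher: any value below 10 meets the condition, and the physician may hold or reduce.
- Baseline below 20: values from B/2 up to 10 do not meet it. As an illustration, B = 16 gives B/2 = 8, so 8 to below 10 is covered by neither the sentence nor the table.

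Even where the condition is met, the sentence allows either a hold or a reduction. It permits a hold but does not supply the missing instruction.

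**3. Does anything else fill it?** The leucovorin rule at 60 ml/min or less presupposes that MTX was given. No other section states a clearance at which MTX is held.

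**4. Renal table with the hold row at below 10.** The rows become above 50, 10 to 50, and below 10. Every clearance of 0 or more falls in exactly one row. With the middle row starting at 10, no other cut-off gives this result: a lower one leaves a gap and a higher one overlaps.

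**5. Bilirubin table.** The rows are below 3.0, 3.1 to 5.0, and above 5.0. With values reported to one decimal place, as the table is written, the only value without a row is exactly 3.0. Making the first row 3.0 or less closes it at that precision.

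**The case against.** The strongest objection is that the point rests on one table cell in text read from a PDF, where a digit can be lost. That cannot be excluded. The other entries in this table and in the liver table look intact, which makes loss less likely but does not settle it. If the signed page reads below 10, the renal point closes.

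The second objection is that, even if the source does read below 0, it is an obvious slip. The table steps down from full dose to half dose to hold, and the row above ends at 10, so few physicians would be misled. This largely stands as to likely harm. It does not justify leaving an unusable stopping threshold in an operative dosing table.

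The third is that safeguards exist. Holding is permitted after a fall of more than 50%, leucovorin is required at 60 ml/min or less, and Section 11.1.4 requires daily creatinine until discharge. This also stands. It reduces the risk without assigning a dose below 10 ml/min.

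A reader might infer that the slip removed a mandatory renal hold, or that MTX cannot be held for renal reasons. The documents support neither: the tables are introduced as guidelines, and the baseline sentence expressly allows holding.

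A reader might also infer that inconsistent holding would distort the mucositis or acute GVHD comparisons. Nothing in the documents lets that be sized. Section 14.0 plans an intent-to-treat analysis because MTX doses may be missed, and Section 7.1 requires every prophylaxis change and its reason to be recorded. That effect would be speculation.

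**Conclusion.** The point holds as a correction to a dosing table. As printed, the hold row can never be met, and 0 to below 10 ml/min has no assigned dose. Patients with a baseline of 20 ml/min or higher are partly covered by the optional hold or reduction. Those with a lower baseline may fall outside both rules, and they should be rare among patients going to myeloablative transplant. The number affected is probably small and cannot be derived from the documents.

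The conclusion assumes that the cell reads the same on the source page. That below 10 was intended is an inference from the adjoining row; the documents do not state it. The bilirubin gap is trivial and is included only because the same edit can close it.

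**What to change.** First check the renal table against the signed protocol page. If the hold row does read below 0:

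- Change it to below 10 ml/min. If the clinical team intended another cut-off, move the lower end of the 50% row to match, so that the two rows still meet.
- In the same edit, change the first bilirubin row to 3.0 mg/dl or less.

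The cost is one corrected cell in each of two tables. No change to the design, sample size or analysis is needed. If the signed page already reads below 10, only the bilirubin edit remains.

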8.0 ADVERSE EVENTS: LIST AND REPORTING REQUIREMENTS

The following is a list of AEs (Section 8.1) and the reporting requirements associated with observed AEs (Sections 8.3 and 8.4).

The clinical course of each event will be followed until resolution, stabilization, or until it is has been determined that the study treatment or participation is not the cause.

Serious adverse events that are still ongoing at the end of the study period will necessitate follow-up to determine the final outcome. Any serious adverse event that occurs after the study period and is considered to be possibly related to the study treatment or study participation will be recorded and reported immediately.

8.1 Adverse Events and Potential Risks

Please refer to the package insert(s) for the comprehensive list of adverse events. Many of these toxicities are recognized toxicities of transplantation and will not be considered adverse effects in the context of this study. For example, re-admissions are common after allogeneic transplantation, and reasons for readmissions most commonly include fever with or without infection. Unless inpatient hospitalizations are thought to be due to one of the study medications, they will not be reported as serious adverse events. Transplant related adverse events which may be influenced by GVHD prophylaxis will be specifically evaluated per secondary objectives (e.g. incidence of renal, liver, and pulmonary toxicities).

8.1.1 Tacrolimus

There are many well described toxic effects of tacrolimus. Primary toxicities in large controlled trials were reversible renal insufficiency, thrombotic microangiopathy, hypertension, hyperglycemia, hypomagnesaemia, hypokalemia, opportunistic infection, and neurologic toxicity. In addition there may be an infusional toxicity from the diluent.

8.1.2 Mycophenolate Mofetil

The use of mycophenolate mofetil has been associated with myelosuppression, increased risk of opportunistic infection and GI toxicity including diarrhea, abdominal pain and vomiting, not related to GVHD. Gastrointestinal bleeding and bowel perforation have been described infrequently.

8.1.3 Methotrexate

The most frequently reported adverse reactions associated with methotrexate use as GVHD prophylaxis include ulcerative stomatitis, leukopenia and suppressed hematopoiesis, hepatic and nephrotoxicity, nausea, and abdominal distress. Other frequently reported adverse effects are malaise, fatigue, chills and fever, and dizziness. Methotrexate may be associated with increased rates of pulmonary complications after transplantation.

8.2 Drug Interactions

8.2.1 Methotrexate

Methotrexate is partially bound to serum albumin, and toxicity may be increased because of displacement by certain drugs, such as salicylates, phenylbutazone, phenytoin and sulfonamides. Renal tubular transport is also diminished by probenecid; use of methotrexate with this drug should be carefully monitored.

Oral antibiotics such as tetracycline, chloramphenicol, and nonabsorbable broad-spectrum antibiotics, may decrease intestinal absorption of methotrexate or interfere with the enterohepatic circulation by inhibiting bowel flora and suppressing metabolism of the drug by bacteria. Penicillins may reduce the renal clearance of methotrexate; increased serum concentrations of methotrexate with concomitant hematologic and gastrointestinal toxicity have been observed with high and low dose methotrexate. Use of methotrexate with penicillins should be carefully monitored.

8.2.2 Mycophenolate Mofetil

MMF activity is decreased with oral administration of antacids and cholestyramine. Acyclovir or ganciclovir blood levels may increase during co-administration with MMF due to competition for tubular secretion of these drugs, especially if renal impairment is present. Probenecid may also augment mycophenolic acid (MPA) levels due to inhibition of tubular secretion. High doses of salicylates (or other highly protein bound drugs) may increase the free fraction of MPA and exaggerate the potential for myelosuppression.

8.2.3 Tacrolimus

Tacrolimus is extensively metabolized by the cytochrome P-450 (CYP3A4) system. Care should be taken when drugs or other substances that are metabolized by CYP3A4 are administered concomitantly with tacrolimus. Grapefruit juice and other drinks containing bergamottin (*Fresca, Squirrt, Sunny Delight*) reduces the CYP3A4-mediated metabolism of tacrolimus and may increase its levels.

Drugs that may increase tacrolimus blood concentrations include:

- Calcium channel blockers: diltiazem, nicardipine, nifedipine, verapamil
- Antifungal agents: ketoconazole, clotrimazole, fluconazole, itraconazole
- Macrolide antibiotics: clarithromycin, erythromycin, troleandomycin
- Gastrointestinal prokinetic agents: cisapride, metoclopramide
- Other drugs: bromocriptine, cimetidine, cyclosporine, danazol, ethinyl estradiol, omeprazole, nefazadone, HIV-protease inhibitors (e.g. ritonavir, indinavir).

Drugs that may decrease tacrolimus concentrations include:

- Anticonvulsants: carbamazepine, phenobarbital, phenytoin
- Antibiotics: rifabutin, rifapentine
- Herbal preparations: St. John's Wort (*hypericum perforatum*) could result in reduced tacrolimus concentrations.

Due to extreme interactions with voriconazole, tacrolimus doses should be lowered by 50% when concomitant therapy with voriconazole is initiated. It is recommended that drugs with known interactions with tacrolimus be avoided when clinically feasible. When these medications are required, dose modifications of tacrolimus may be required.

8.2 Definitions

8.2.1 Adverse Events

An **adverse event (AE)** is any unfavorable or unintended event, physical or psychological, associated with a research study, which causes harm or injury to a research participant as a result of the participant's involvement in a research study. The event can include abnormal laboratory findings, symptoms, or disease associated with the research study. The event does not necessarily have to have a causal relationship with the research, any risk associated with the research, the research intervention, or the research assessments.

Adverse events may be the result of the interventions and interactions used in the research; the collection of identifiable private information in the research; an underlying disease, disorder, or condition of the subject; and/or other circumstances unrelated to the research or any underlying disease, disorder, or condition of the subject.

External adverse events are adverse events experienced by subjects enrolled in multicenter clinical trials at sites other than the site(s) over which the Institutional Review Board has jurisdiction.

Internal adverse events are adverse events experienced by subjects enrolled at the site(s) under the IRB's jurisdiction for either multicenter or single-center research projects.

8.2.2 **The significance of an adverse event** is used to describe the patient/event outcome or action criteria associated with events that pose a threat to a patient's life or functioning (i.e., moderate, severe or life threatening). Based on the National Cancer Institute Guidelines for the Cancer Therapy Evaluation Program, severity can be defined by the following grades of events:

Grades 1 are mild adverse events (e.g., minor event requiring no specific medical intervention; asymptomatic laboratory findings only; marginal clinical relevance).

Grades 2 are moderate adverse events (e.g., minimal intervention; local intervention; non-invasive intervention; transfusion; elective interventional radiological procedure; therapeutic endoscopy or operation).

Grades 3 are severe and undesirable adverse events (e.g., significant symptoms requiring hospitalization or invasive intervention; transfusion; elective interventional radiological procedure; therapeutic endoscopy or operation).

Grades 4 are life threatening or disabling adverse events (e.g., complicated by acute, life-threatening metabolic or cardiovascular complications such as circulatory failure, hemorrhage, sepsis; life-threatening physiologic consequences; need for intensive care or emergent invasive procedure; emergent interventional radiological procedure, therapeutic endoscopy or operation).

Grades 5 are fatal adverse event resulting in death.

8.2.3 Serious Adverse Events

A **serious adverse event (SAE)** is any adverse experience occurring at any dose that results in any of the following outcomes:

- **Results in death.**
- Is a **life-threatening** adverse experience. The term **life-threatening** in the definition of serious refers to an adverse event in which the subject was at risk of death at the time of the event. It does not refer to an adverse event which hypothetically might have caused death if it were more severe.
- Requires **inpatient hospitalization or prolongation of existing hospitalization**. Any adverse event leading to hospitalization or prolongation of hospitalization will be considered as Serious, UNLESS at least one of the following expectations is met:
 - The admission results in a hospital stay of less than 12 hours OR
 - The admission is pre-planned (i.e., elective or scheduled surgery arranged prior to the start of the study) OR
 - The admission is not associated with an adverse event, please refer to Section 8.1.
 - However it should be noted that **invasive treatment during any hospitalization may fulfill the criteria of “medically important”** and as such may be reportable as a serious adverse event dependant on clinical judgment. In addition where local regulatory authorities specifically require a more stringent definition, the local regulation takes precedent.
- Results in **persistent or significant disability/incapacity**. The definition of disability is a substantial disruption of a person’s ability to conduct normal life’s functions.
- Is a **congenital anomaly/birth defect**.
- Is an **important medical event**. Important medical events that may not result death, be life-threatening, or require hospitalization may be considered a serious adverse experience when, based upon appropriate medical judgment, they may jeopardize the patient or subject and may require medical or surgical intervention to prevent one of the outcomes listed in this definition. Examples of such medical events include allergic bronchospasm requiring intensive treatment in an emergency room or at home, blood disease or disorders, or convulsions that do not result in inpatient hospitalization, or the development of drug dependency or drug abuse.

8.2.4 Expectedness

Adverse Events can be Expected or Unexpected.

An **expected adverse event** is an event previously known or anticipated to result from participation in the research study or any underlying disease, disorder, or condition of the

subject. The event is usually listed in the Investigator Brochure, consent form or research protocol.

An unexpected adverse event is an adverse event not previously known or anticipated to result from the research study or any underlying disease, disorder, or condition of the subject.

8.2.5 Attribution

Attribution is the relationship between an adverse event or serious adverse event and the study drug. Attribution will be assigned as follows:

- Definite – The AE is clearly related to the study drug.
- Probable – The AE is likely related to the study drug.
- Possible – The AE may be related to the study drug.
- Unlikely – The AE is doubtfully related to the study drug.
- Unrelated – The AE is clearly NOT related to the study drug.

8.3 Reporting Procedures for All Adverse Events

All participating investigators will assess the occurrence of AEs throughout the subject's participation in the study. Subjects will be followed for toxicity for 30 days after treatment with tacrolimus or mycophenolate has been discontinued, tapered or until death, whichever occurs first. If patient continues on tacrolimus or mycophenolate for treatment of continued GVHD past the endpoint of study (1 year after infusion of HCT), adverse events will no longer be reported. The clinical course of each event will be followed until resolution, stabilization, or until it has been determined that the study treatment or participation is not the cause.

Toxicities of the blood/bone marrow, gut, liver and skin will be evaluated separately since they are likely to be affected by GVHD. GVHD severity will be determined clinically, however biopsies of affected are strongly encouraged whenever possible.

Grade 4-5 serious adverse events will be reported according to the local IRB's policies and procedures.

The investigator is responsible for ensuring that serious adverse events observed by the investigator or reported by the subject which occur after the subject has started treatment with the first study drug (day -1) are fully recorded in the subject's case report form, subject's medical records, and/or any other institutional requirement. Specific toxicities, including laboratory values and events outlined in secondary objectives will be captured per protocol; and will not necessarily be considered as part of adverse event reporting as these are expected toxicities post transplant, but may be influenced by GVHD and GVHD prevention approaches. Source documentation must be available to support all adverse events.

The investigator will provide the following for serious adverse events:

- Description of the event
- Grade of toxicity
- Attribution of relatedness to the investigational agent

In this study, descriptions and grading scales found in the NCI Common Terminology Criteria for Adverse Events (CTCAE) version 4.0 available at <http://ctep.cancer.gov> will be utilized for AE reporting.

Investigative sites will report adverse events to their respective IRB according to the local IRB's policies and procedures in reporting adverse events.

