3.4.2 Duration of Follow Up

Patients will be followed for 1 year after T-0 (date of infusion of HCT) or until death, whichever occurs first.

The clinical course of each event will be followed until resolution, stabilization, or until it has been determined that the study treatment or participation is not the cause.

Serious adverse events that are still ongoing at the end of the study period will necessitate follow-up to determine the final outcome. Any serious adverse event that occurs after the study period and is considered to be possibly related to the study treatment or study participation will be recorded and reported immediately.

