8.4 Serious Adverse Event Reporting Procedures

Serious adverse events that occur beginning with the first day of the study drug administration, during treatment, or within 30 days of the last dose of treatment, or up to study end point must be reported to the Cleveland Clinic Principal Investigator.

Investigative sites will report serious adverse events to their respective IRB according to the local IRB's policies and procedures in reporting serious adverse events.

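### Section 8.3 can be read to end toxicity follow-up when either drug stops, which on the planned schedule is 80 days earlier in Group B, and it conflicts with its own first sentence and with Section 8.4

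*Combined protocol and SAP*

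**What the plan says.** **End of follow-up.** Section 8.3 gives two rules in consecutive sentences. The first is general: "All participating investigators will assess the occurrence of AEs throughout the subject's participation in the study". Section 3.4.2 sets the length of participation: "Patients will be followed for 1 year after T-0 (date of infusion of HCT) or until death, whichever occurs first". The second rule in 8.3 is linked to the drugs: "Subjects will be followed for toxicity for 30 days after treatment with tacrolimus or mycophenolate has been discontinued, tapered or until death, whichever occurs first". A third sentence ends adverse event reporting at 1 year for patients still taking either drug for GVHD.

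Section 8.4 uses another clock for serious adverse events. Those occurring during treatment, or "within 30 days of the last dose of treatment, or up to study end point must be reported", go to the lead investigator.

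**Drug schedule without GVHD.** Under Section 6.1.2, Group B alone receives MMF, and "MMF may be tapered after day +45 and stopped by day +100". Under Section 6.1.1, both groups receive tacrolimus, and "Tac may start to be tapered approximately at day +100 and should be tapered off by day +180".

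**Start of recording.** Section 8.3 has serious events recorded when they occur "after the subject has started treatment with the first study drug (day -1"). Section 6.1.1 also allows "tacrolimus 0.03mg/kg/dose BID orally beginning on day -3". Section 8.4 starts from the first day a study drug is given and names no day number.

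**The concern.** The 30-day rule names two drugs joined by *or*, and one of them is given in one arm only. A site that follows the sentence literally can stop recording toxicity in a Group B patient 30 days after MMF ends, while that patient is still on tacrolimus. In Group A only stopping tacrolimus can start the clock. Both arms carry tacrolimus toxicity, so recorded events could then differ between arms because the collection time differs. The shorter window would fall on the experimental three-drug arm.

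The events exposed are those that reach the database only through 8.3: non-serious events that are neither secondary endpoints nor captured elsewhere. Non-serious hypertension and neurologic toxicity, both named for tacrolimus in Section 8.1.1, are examples. Sites could also differ from one another, because each of the three rules can be followed in good faith.

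**Working it through.** The documents state no window length per arm, so there is no figure to reproduce. The check is calendar arithmetic on the planned stop days.

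**Inputs.** Tacrolimus: taper from about day 100, off by day 180 (6.1.1). MMF, Group B only: taper after day 45, stopped by day 100 (6.1.2). Tail: 30 days (8.3). Participation: 1 year, taken as day 365 (3.4.2). Assumed: no GVHD, no early stop, no death.

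**Formula.** End of follow-up = trigger day + 30.

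| Reading | Group A ends | Group B ends | Difference |
|---|---|---|---|
| Either drug stopped | 180 + 30 = day 210 | 100 + 30 = day 130 | 80 days (80/210 = 38%) |
| Either drug starts its taper | 100 + 30 = day 130 | 45 + 30 = day 75 | 55 days (55/130 = 42%) |
| Last drug stopped | 180 + 30 = day 210 | 180 + 30 = day 210 | 0 |
| Participation or study end point | day 365 | day 365 | 0 |

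The arms differ only if stopping or tapering MMF alone is enough to start the clock. The second row also takes *tapered* to mean that the taper has begun. A completed taper is the more natural sense, so that row is a limiting case.

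**Which data depend on 8.3.**

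- Serious adverse events: 8.4 counts from the last dose or runs to the study end point. The last planned drug is tacrolimus in both arms, so the end does not depend on the arm.
- Renal, hepatic and pulmonary function: Section 11.1.5 has organ toxicity assessed at least weekly to day 100 and then at visits to 1 year.
- Infections: recorded for 1 year (11.1.5).
- Secondary-objective toxicities: 8.3 itself captures these apart from adverse event reporting.
- Blood and marrow, gut, liver and skin: 8.3 has these evaluated separately, so gut toxicity and myelosuppression are weak examples of lost events.
- What remains: non-serious events outside these groups.

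**Start.** For a patient on oral tacrolimus, the first study drug is given on day -3. The day number in 8.3 leaves out days -3 and -2, whereas 8.4 includes them. Both groups may take oral tacrolimus, so this conflict is not tied to the arm.

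**The case against.** The strongest case against the point is that it depends on one reading of a loose sentence. The closing first-to-occur phrase follows death, so it most naturally chooses between the 30-day point and death, not between the two drugs. The sentence before it calls for assessment throughout participation. The sentence after it addresses patients who continue either drug past 1 year, which suggests that reporting goes on while either is taken. The last-drug and participation readings both give no difference between arms. Section 14.0 plans no general comparison of adverse events, and the planned complication endpoints use fixed windows equal in both arms.

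Most of this stands. A reader might infer that adverse events *are* collected for a much shorter time in Group B, but the documents do not establish that. A reader might also infer that a planned safety comparison would favour Group B. None of the comparisons in Section 14.0, and none of the toxicity and infection parameters in Section 12.4, rests on the 30-day rule.

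The objection does not remove the conflict. Even if the closing phrase refers only to death, the trigger is still that one drug *or* the other has been stopped, and stopping MMF meets it. The last-drug reading needs a word that 8.4 has and 8.3 lacks. If participation simply governed, the 30-day sentence would do nothing. The day -1 mismatch is minor, since 8.4 already starts from the first dose, but the two sections still disagree.

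**Conclusion.** The concern holds as a conflict between collection rules, one of which can make the recording of non-serious events depend on the assigned arm. On that reading Group B's follow-up ends 80 days earlier (day 130 against day 210). On the other defensible readings the difference is zero. High confidence is justified in the inconsistency, but much less in any resulting bias.

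The 80 days come from the planned schedule and are not an expected average. Stop days are discretionary and apply without GVHD. Section 14.0 gives a current rate of 62% for any acute GVHD by day 60, and Section 6.2.10 generally continues both drugs while acute GVHD is treated, so the planned days will not apply to many patients. It is tempting to read the 38% shorter window as 38% fewer recorded events. That would need a constant event rate, which the documents do not support: conditioning, the methotrexate doses (days +1 to +11) and engraftment all fall early.

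The harm is therefore confined to descriptive reporting of non-serious events outside the tracked endpoints, plus a two-day disagreement on when recording of serious events starts for patients on oral tacrolimus. It should be corrected, but it does not threaten the primary or planned secondary analyses.

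**What to change.** Put one collection window, in the same words, in Sections 8.3 and 8.4: adverse and serious adverse events are recorded in both groups from the first dose of any study drug until the 1-year study end point or death. Delete the day -1 parenthesis, so that the start follows each patient's actual first dose, and remove the 30-day sentence.

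If a drug-based end is kept for non-serious events, run the 30 days from the last of all study drugs stopped, and say whether a taper counts from its start or its completion. Limit any between-arm summary of adverse events to a stated common day, because patient-level windows will still vary. A fixed day-210 cut-off is not a good substitute: it would shorten the 1-year window that 8.3 and 3.4.2 already imply.

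The cost is amended wording in two sections and some added recording of non-serious events. Measured against the narrowest stop-based reading, that is up to 365 − 130 = 235 more days in Group B and 365 − 210 = 155 in Group A. Against the participation reading it adds nothing. No new visits are needed, since Section 11.1.4 already schedules organ toxicity assessment at visits to 1 year.
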